D. Summary of Rationale	Based on previous studies, pembrolizumab may be an effective treatment for patients with solid tumors. The purpose of this study is to determine whether the addition of pembrolizumab to doxorubicin will yield an acceptable response rate in subjects with advanced soft tissue sarcoma. We will also examine if PD-L1 expression in sarcoma can predict for therapeutic response to pembrolizumab in subjects with soft tissue sarcoma.
E. Study Objectives	The primary objective of this study is to assess the safety and toxicity profile of doxorubicin and pembrolizumab in previously treated or untreated subjects with unresectable or metastatic soft tissue sarcoma. The secondary objectives are to assess overall survival, response rate, duration of response, and progression-free survival with this regimen using RECIST 1.1 criteria. The exploratory objectives are to assess PFS, ORR, DoR, and DCR using the immune-related RECIST (irRECIST) criteria, evaluate the correlation between PD-L1 expression levels and antitumor activity of MK-3475, investigate other biomarkers that may correlate with tumor responses, evaluate differences in tumor tissue characteristics in biopsies taken during treatment with MK-3475 versus baseline, and evaluate ORR and PFS after second course treatment of pembrolizumab.
F. Sample	≤ 30 subjects
G. Inclusion/Exclusion	
 • Recurrent/metastatic soft tissue sarcoma not appropriate for surgical therapy. • No prior anthracycline and/or immunotherapy. • ECOG 0 to 1 with normal organ function.
H. Dosage/ Dosage Form, Route, And Dose Regimen	Pembrolizumab 200 mg will be delivered by 30 minute IV infusion every 3 weeks until progression. Subjects 12-17 years of age will receive pembrolizumab at 2 mg/kg IV (up to 200 mg) every 3 weeks until progression. Doxorubicin 60-75 mg/m ² will be delivered by IV infusion per institutional protocol (infusion, IV push) every 3 weeks until progression. Subjects will receive doxorubicin 60 mg/m ² IV on Cycle 1 Day 1. Escalation to 75 mg/m ² is allowed after Cycle 1 per investigator discretion. Re-initiation of pembrolizumab after discontinuation and presence of progressive disease is an additional option. Total dose of doxorubicin should not exceed cumulative lifetime dose of 450 mg/m ² .
I. Statistical Analysis	Previous reports have demonstrated that the rate of any severe or life-threatening toxicity with a median of 3 courses of doxorubicin and dacarbazine every 3 weeks is 55%. If it becomes evident that the rate of severe or life-

	
threatening toxicity convincingly exceeds 55%, the study will be halted. Response rates will be calculated with corresponding 95% confidence intervals based on the Clopper-Pearson method. Duration of response and PFS distributions will be estimated using Kaplan-Meier techniques. Exploratory correlative analyses will be conducted on biomarkers using logistic regression (response rate) and Cox proportional hazards models (duration of response and PFS). Incident rates for adverse events, SAEs, and deaths on study therapy will be summarized.

--	--

SCHEMA

* Subjects 12-17 years of age will receive pembrolizumab 2 mg/kg IV (up to 200 mg) every 3 weeks

LIST OF ABBREVIATIONS

Abbreviation	Definition of Term
AE	Adverse event
ALT	Alanine aminotransferase
aPTT	Activated partial thromboplastin time
AST	Aspartate aminotransferase
CI	Confidence interval
CHF	Congestive heart failure
CFR	Code of Federal Regulations
CNS	Central nervous system
CR	Complete response
CT	Computed tomography
CTCAE	Common Terminology Criteria for Adverse Events
CTMS	Clinical trial management system
CrCl	Creatinine clearance
DCSI	Development Core Safety Information
DNA	Deoxyribonucleic acid
DSMC	Data and Safety Monitoring Committee
eCRF	Electronic case report form
ECG	Electrocardiogram
ECI	Events of clinical interest
ECHO	Echocardiogram
ECOG	Eastern Cooperative Oncology Group
FDA	Food and Drug Administration
FSH	Follicle-stimulating hormone
GCP	Good Clinical Practice

G-CSF	Granulocyte-colony stimulating factor
GIST	Gastrointestinal stromal tumor
GMP	Good Manufacturing Practices
HIV	Human immunodeficiency virus
IB	Investigator brochure
IDS	Investigational drug services
IHC	Immunohistochemistry
INR	International normalized ratio
IRB	Institutional Review Board
irRC	Immune related response criteria
IV	Intravenous
LCI	Levine Cancer Institute
LVEF	Left ventricular ejection fraction
mAb	Monoclonal antibody
MEL	Melanoma
MRI	Magnetic resonance imaging
MUGA	Multigated acquisition scan
NSCLC	Non-small cell lung cancer
ORR	Objective response rate
OTC	Over the counter
PI	Principal Investigator
PK	Pharmacokinetics
PR	Partial response
PT	Partial thromboplastin
Q2W	Every two weeks
Q3W	Every three weeks
RCC	Renal cell carcinoma

RNA	Ribonucleic acid

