1.4. Exploratory Objectives

The exploratory objectives of this study include:

- Assessment of PFS, ORR, and DoR, using the immune-related RECIST (irRECIST) criteria
 - Analyze immune response endpoints
 - Concordance analysis relative to standard RECIST
 - Evaluate impact of treating after progression to see impact on concordance
- Evaluate the correlation between PD-L1 expression levels and antitumor activity of MK-3475
- Investigate other biomarkers (e.g. tumor infiltrating lymphocytes) that may correlate with tumor responses
- Evaluate differences in tumor tissue characteristics in biopsies taken during treatment with MK-3475 versus baseline
- Evaluate objective response rate to second course treatment of pembrolizumab
- Evaluate progression-free survival after second course treatment of pembrolizumab (PFS2)

Whole blood samples will also be collected at baseline for germ line DNA analysis in select subjects for extended genomic analysis.

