3. SUBJECT SELECTION

3.1. Subject Accrual

A maximum of 30 subjects with soft tissue sarcoma will be enrolled as a single cohort over a 24-month period. Both men and women of all races and ethnic groups are eligible for this trial.

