4. INVESTIGATIONAL PLAN

4.1. Overall Study Design

This is a single arm phase II study designed to investigate the safety, tolerability, and preliminary efficacy of the combination of pembrolizumab and doxorubicin in subjects with metastatic/unresectable soft tissue sarcoma. Following informed consent and eligibility check, all enrolled subjects will receive therapy with doxorubicin and pembrolizumab.

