12. STATISTICAL CONSIDERATIONS

12.1. Sample Size

This study is primarily designed to assess the safety of doxorubicin (60-75 mg/m²) and pembrolizumab (200 mg) in previously treated or untreated subjects with

unresectable or metastatic soft tissue sarcoma. Based on the Bayesian stopping rules described in Section 12.5, 30 subjects will enable an assessment regarding whether or not the severe or life-threatening treatment emergent adverse event rate convincingly exceeds 0.55.⁴⁸

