12.5. Primary Analysis

A maximum of 30 evaluable subjects with soft tissue sarcoma will be enrolled as a single cohort. It is not anticipated that the addition of pembrolizumab to standard chemotherapy will increase the rate of severe or life-threatening toxicity. It has been reported that the rate of any severe or life-threatening toxicity of doxorubicin and dacarbazine every 3 weeks is 55%⁴⁸.

If it becomes evident that the rate of severe or life-threatening toxicity convincingly exceeds 55%, enrollment to the study will be halted.

The stopping rule will hold enrollment if the posterior probability of severe or life-threatening toxicity risk exceeding 0.55 is 75% or higher. In this event, data will be evaluated to inform the subsequent conduct of the study. The prior for this monitoring rule is beta (11,9). This means that our prior assumption regarding the proportion of severe or life-threatening toxicity is 0.55, and there is 90% probability that this proportion is between 0.368 and 0.726. The operating characteristics of the stopping rule are given in Table 11 and are based on 5000 simulations:

Table 11. Operating characteristics of the stopping rule

Number of Subjects with Severe or Life-Threatening Toxicities	Max. Denominator Cutoff for Early Stopping	Posterior Probability: $\Pr(\text{Risk} > 0.55 \text{Data})$
4	4	0.7834
5	6	0.7536
6	7	0.8056
7	9	0.7728
8	11	0.7694
9	13	0.7558
10	14	0.7944
11	16	0.7812
12	18	0.7592
13	19	0.8002
14	21	0.7818
15	23	0.7710
16	25	0.7594
17	26	0.7988
18	28	0.7828
19	30	0.7706

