12.8. Exploratory Analyses

Analysis of objective response, duration of response, and PFS whereby the endpoints are based on irRECIST will be conducted using methods as described in Section 12.6. Correlative analysis will be conducted on PD-L1 and other biomarkers using logistic regression for objective response and Cox proportional hazards models for time to event endpoints. Other exploratory analysis will be conducted as deemed necessary. Summaries of second course objective response rate and progression free survival will be conducted.

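### The PD-L1 analysis can show association with outcome on doxorubicin plus pembrolizumab, not prediction of response to pembrolizumab; its coding and small-sample method should also be stated

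*Combined protocol and SAP*

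**What the plan says.** The Summary of Rationale in the protocol summary gives, beside the main purpose, the aim to "examine if PD-L1 expression in sarcoma can predict for therapeutic response to pembrolizumab". Section 1.4 lists it as exploratory: "Evaluate the correlation between PD-L1 expression levels and antitumor activity of MK-3475".

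On design, section 4.1 states: "This is a single arm phase II study designed to investigate the safety, tolerability, and preliminary efficacy", and that "all enrolled subjects will receive therapy with doxorubicin and pembrolizumab". Section 3.1 caps enrolment: "A maximum of 30 subjects with soft tissue sarcoma will be enrolled as a single cohort". Section 12.1 justifies that number by toxicity alone: "30 subjects will enable an assessment regarding whether or not the severe or life-threatening treatment emergent adverse event rate convincingly exceeds 0.55".

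On analysis, section 12.8 states: "Correlative analysis will be conducted on PD-L1 and other biomarkers using logistic regression for objective response and Cox proportional hazards models". Section 12.6 plans the same model types for baseline characteristics and selected biomarkers as secondary correlative analyses, including Cox models for duration of response. The Statistical Analysis item of the protocol summary repeats the biomarker models and calls them exploratory. Under section 12.3, response is analysed only in subjects with measurable disease, and duration of response only in responders; section 3.2.1 also admits subjects with non-measurable disease.

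The documents give no PD-L1 cut-point or coding, expected PD-L1 prevalence, expected number of responders, or penalised or exact method.

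**The concern.** A marker predicts response to pembrolizumab if the benefit that pembrolizumab adds differs by marker level. To see that, one needs outcomes with and without pembrolizumab at each level. Here there are only outcomes with both drugs. If PD-L1-positive subjects respond more often, they may have more favourable disease, be more sensitive to doxorubicin, or benefit more from pembrolizumab. At stake is the sentence in the final report: the objective as worded invites a claim about pembrolizumab that the data cannot carry.

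The second matter is estimation. With few subjects, a binary marker may have no responders, or only responders, in one of its groups. The maximum-likelihood odds ratio is then zero or infinite, and the usual interval is meaningless. A plan that leaves the coding open does not rule this out and does not say what will be reported if it happens.

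**Working it through.** **1. The plan's own figure.** The only numerical basis for 30 subjects is the toxicity rule in section 12.5. With prior Beta(11, 9) and 19 events in 30, the posterior is Beta(11 + 19, 9 + 11) = Beta(30, 20), and Pr(risk > 0.55) = 0.767; Table 11 gives 0.7706. All 16 rows agree within 0.014, and the stated 90% prior interval of 0.368 to 0.726 reproduces. The sample size is therefore sound on its own terms, but nothing in it concerns PD-L1.

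**2. What the design identifies.** Write p(M, T) for the response probability at marker level M under treatment T. The predictive question concerns

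[p(+, doxorubicin + pembrolizumab) − p(+, doxorubicin)] − [p(−, doxorubicin + pembrolizumab) − p(−, doxorubicin)].

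The trial observes the first term in each bracket and never the second. As an assumed example, let response on the combination be 40% in positives and 10% in negatives, an odds ratio of (0.40/0.60)/(0.10/0.90) = 6.

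- If doxorubicin alone would have given 40% and 10%, pembrolizumab adds nothing in either group. PD-L1 is then purely prognostic or a marker of doxorubicin sensitivity.
- If doxorubicin alone would have given 10% in both, pembrolizumab adds 30 points in positives and none in negatives. PD-L1 is then purely predictive.

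Both cases produce the same data and the same odds ratio. The doxorubicin term cannot be taken as negligible: section 2.2.3 quotes 9% + 32% = 41% for the single agent in 36 patients, which on 30 subjects is 0.41 × 30 ≈ 12 responses.

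**3. When logistic regression has no finite estimate.** For a binary marker, this happens when any cell of the 2×2 table is zero. With n₁ positives responding at p₁ and n₂ negatives at p₂,

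Pr(zero cell) = 1 − [1 − p₁^n₁ − (1 − p₁)^n₁] × [1 − p₂^n₂ − (1 − p₂)^n₂].

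Group sizes and response rates are assumptions, except the 41%, which is the documents' doxorubicin figure.

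| Positives / negatives | Response rates | Odds ratio | Pr(zero cell) |
|---|---|---|---|
| 6 / 24 | 20% / 20% | 1 | 26.6% |
| 6 / 24 | 41% / 41% | 1 | 4.7% |
| 15 / 15 | 40% / 10% | 6 | 20.6% |
| 15 / 15 | 35% / 5% | 10.2 | 46.4% |

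First row: 0.8^6 = 0.2621, 0.2^6 = 0.0001, 0.8^24 = 0.0047, so 1 − 0.7378 × 0.9953 = 0.266. Second row: 0.59^6 = 0.0422, 0.41^6 = 0.0048, and the negatives contribute almost nothing, so 0.047.

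The same check can be made with the number of responders fixed, no association and 30 subjects (hypergeometric):

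| PD-L1 positives | 5 responders | 8 responders | 11 responders |
|---|---|---|---|
| 3 | 57% | 39% | 28% |
| 6 | 30% | 13% | 5% |
| 10 | 11% | 2% | 0.3% |
| 15 | 4% | 0.2% | <0.1% |

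For an untied continuous score with no association, separation needs all responders at one end: 2/C(30, r). At r = 5 this is 2/142,506 = 0.0014%, and less for 8 or 11 responders. A score with many ties at zero lies between: 2% to 16% with 70% zeros and 10% to 33% with 80% zeros, by simulation.

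**4. Cox models.** For duration of response only responders count. If all of them share one marker level, no hazard ratio exists. With 5 responders, 20% prevalence and no association, that alone has probability 0.8^5 + 0.2^5 = 0.328; with 12 responders it is 0.8^12 = 0.069.

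**5. Precision when the estimate is finite.** At 30 subjects, two-sided 5%, prevalence 20% to 50% and overall response 17% to 37% (all assumed), power is 18% to 28% for an odds ratio of 3 and 30% to 51% for 5.

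**The case against.** The objective is exploratory, section 1.4 speaks of correlation rather than prediction, and no test, decision or sample size depends on PD-L1. This stands, and it limits the weight of the point. It does not remove it: an exploratory label excuses imprecision, but both the summary and section 1.4 still name a quantity that the design does not identify.

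Pembrolizumab is also given alone, after doxorubicin stops and in the Second Course Phase (sections 6.1 and 7). Those subjects are selected by how they fared on the combination and have no comparator, so they do not supply the missing term.

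A reader might infer that logistic regression will often have no finite estimate here, or will fail just when PD-L1 matters most. The documents do not support that. It needs a dichotomised marker with few positives, few responders, or odds ratios of about 6 to 10. At 41% overall response and 15 positives against 15 negatives, the zero-cell chance is under 1% at an odds ratio of 3 and about 2% at 5. Section 1.4 refers to expression levels, which may mean a continuous score. Responder counts such as 5 to 11, or about 27 subjects with measurable disease, are assumptions too.

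A reader might also infer that a multivariable model is planned; none is specified. Finally, Firth and exact fits are forms of logistic regression, and section 12.8 leaves room for further exploratory analysis, so the plan permits them. It does not say they will be used.

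**Conclusion.** The attribution point holds on the documents and needs no numerical assumption: PD-L1 can be related to outcome on doxorubicin plus pembrolizumab, and prognostic and predictive effects cannot be told apart.

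The estimation point holds conditionally: the models can fail to give a finite estimate. With 6 positives among 30 and no association, the chance is about 27% at 20% response and about 5% at 41%; it is practically nil for an untied continuous score. These figures rest on assumed prevalence, response rates and dichotomisation. The real gap is that the coding is not stated. A finite estimate would still be imprecise.

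Severity is minor. The primary toxicity analysis and the sample size are unaffected.

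**What to change.** 1. In the Summary of Rationale and section 1.4, reword the objective as *association of PD-L1 expression with outcome on doxorubicin plus pembrolizumab; prognostic and predictive effects cannot be separated*.
2. State the PD-L1 coding before the data are examined, continuous where possible; if a cut-point is used, name it.
3. In sections 12.6 and 12.8, specify Firth-penalised (or exact) logistic regression and Firth-penalised Cox models. Use profile-likelihood intervals for the penalised fits. Carry the same wording into the Statistical Analysis item of the summary.
4. Label any Cox model for duration of response as descriptive. The Kaplan-Meier estimate is already planned. Dropping the Cox model altogether would be a reasonable preference but is not required.

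The cost is a few lines of text and a software option, with no new subjects, samples or procedures. The price is a more modest claim and slight shrinkage of the estimates.

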1. OBJECTIVES

1.1. Primary Objective

The primary objective of this study is to evaluate the severe and life-threatening toxicity rate observed in metastatic or unresectable soft tissue sarcoma subjects treated with doxorubicin and pembrolizumab, and compare to historical control.

1.2. Secondary Objectives

The secondary objectives are to assess overall survival (OS), and objective response rate (ORR), duration of response (DoR), and progression-free survival (PFS) with this regimen using RECIST 1.1 criteria.

1.3. Safety Objectives

To assess treatment administration, safety, tolerability and adverse event profile of doxorubicin and pembrolizumab.

1.4. Exploratory Objectives

The exploratory objectives of this study include:

- Assessment of PFS, ORR, and DoR, using the immune-related RECIST (irRECIST) criteria
 - Analyze immune response endpoints
 - Concordance analysis relative to standard RECIST
 - Evaluate impact of treating after progression to see impact on concordance
- Evaluate the correlation between PD-L1 expression levels and antitumor activity of MK-3475
- Investigate other biomarkers (e.g. tumor infiltrating lymphocytes) that may correlate with tumor responses
- Evaluate differences in tumor tissue characteristics in biopsies taken during treatment with MK-3475 versus baseline
- Evaluate objective response rate to second course treatment of pembrolizumab
- Evaluate progression-free survival after second course treatment of pembrolizumab (PFS2)

Whole blood samples will also be collected at baseline for germ line DNA analysis in select subjects for extended genomic analysis.

2. BACKGROUND AND RATIONALE

2.1. Study Disease

Sarcomas are a heterogeneous group of rare, malignant tumors, with over 50 histologic subtypes¹ which are generally categorized as bone and soft tissue sarcomas. The exact incidence of soft tissue sarcoma is not precisely known. A recent study in the Rhone-Alps region in France identified 748 new cases in a cohort of roughly 6 million residents². The estimated world age-standardized incidence rate was, 4.8/100,000, which was higher than previously reported (1-3/100,000). Historically, soft tissue sarcomas have been treated similarly. Doxorubicin-based chemotherapy has been the first line standard of care for more than 20 years. Adding additional cytotoxic agents (e.g. ifosfamide, dacarbazine) to doxorubicin improves response rates, but at the expense of increased toxicity and no clear increase in survival. Some histologic subtypes respond better than others. Anti-angiogenic and targeted therapies (e.g. sunitinib) to this point have been of marginal benefit in the treatment of soft tissue sarcomas. Further progress is needed.

2.2. Experience with Pembrolizumab

2.2.1. Pharmaceutical and Therapeutic Background

The importance of intact immune surveillance in controlling outgrowth of neoplastic transformation has been known for decades³. Accumulating evidence shows a correlation between tumor-infiltrating lymphocytes (TILs) in cancer tissue and favorable prognosis in various malignancies⁴⁻³⁷. In particular, the presence of CD8⁺ T-cells and the ratio of CD8⁺ effector T-cells / FoxP3⁺ regulatory T-cells seems to correlate with improved prognosis and long-term survival in solid malignancies such as ovarian, colorectal and pancreatic cancer, hepatocellular carcinoma, malignant melanoma (MEL) and renal cell carcinoma (RCC). TILs can be expanded ex vivo and re-infused, inducing durable objective tumor responses in cancers such as MEL^{38,39}. The PD-1 receptor-ligand interaction is a major pathway hijacked by tumors to suppress immune control. The normal function of PD-1, expressed on the cell surface of activated T-cells under healthy conditions, is to down-modulate unwanted or excessive immune responses, including autoimmune reactions. PD-1 (encoded by the gene *Pdcd1*) is an Ig superfamily member related to CD28 and CTLA-4 which has been shown to negatively regulate antigen receptor signaling upon engagement of its ligands (PD-L1 and/or PDL2). The structure of murine PD-1 has been resolved. PD-1 and family members are type I transmembrane glycoproteins containing an Ig Variable-type (V-type) domain responsible for ligand binding and a cytoplasmic tail which is responsible for the binding of signaling molecules. The cytoplasmic tail of PD-1 contains 2 tyrosine-based signaling motifs, an immunoreceptor tyrosine-based inhibition motif (ITIM) and an immunoreceptor tyrosine-based switch motif (ITSM). Following T-cell stimulation, PD1 recruits the tyrosine phosphatases SHP-1 and SHP-2 to the ITSM motif within its cytoplasmic tail, leading to the dephosphorylation of effector molecules such as CD3 ζ , PKC θ and ZAP70 which are involved in the CD3 T-cell signaling cascade. The

mechanism by which PD-1 down modulates T-cell responses is similar to, but distinct from that of CTLA-4 as both molecules regulate an overlapping set of signaling proteins. PD-1 was shown to be expressed on activated lymphocytes including peripheral CD4⁺ and CD8⁺ T-cells, B-cells, T regs and Natural Killer cells. Expression has also been shown during -thymic development on CD4-CD8- (double negative) T-cells as well as subsets of macrophages and dendritic cells. The ligands for PD-1 (PD-L1 and PD-L2) are constitutively expressed or can be induced in a variety of cell types, including non-hematopoietic tissues as well as in various tumors. Both ligands are type I transmembrane receptors containing both IgV- and IgC--like domains in the extracellular region and contain short cytoplasmic regions with no known signaling motifs. Binding of either PD-1 ligand to PD-1 inhibits T-cell activation triggered through the T-cell receptor. PD-L1 is expressed at low levels on various non-hematopoietic tissues, most notably on vascular endothelium, whereas PD-L2 protein is only detectably expressed on antigen-presenting cells found in lymphoid tissue or chronic inflammatory environments. PD-L2 is thought to control immune T-cell activation in lymphoid organs, whereas PD-L1 serves to dampen unwarranted T-cell function in peripheral tissues. Although healthy organs express little (if any) PD-L1, a variety of cancers were demonstrated to express abundant levels of this T-cell inhibitor. PD-1 has been suggested to regulate tumor-specific T-cell expansion in subjects with melanoma (MEL). This suggests that the PD-1/PD-L1 pathway plays a critical role in tumor immune evasion and should be considered as an attractive target for therapeutic intervention.

Pembrolizumab is a potent and highly selective humanized monoclonal antibody (mAb) of the IgG4/kappa isotype designed to directly block the interaction between PD-1 and its ligands, PD-L1 and PD-L2. Keytruda (pembrolizumab) has recently been approved in the United States for the treatment of patients with unresectable or metastatic melanoma and disease progression following ipilimumab and, if BRAF V600 mutation positive, a BRAF inhibitor.

